## List of Abbreviations

3D CRT	3 Dimension Conformal External Beam Radiation Therapy
ACD	ASTRO Consensus Definition
ADR	Adverse Drug Reaction
AE	Adverse Event
ASTRO	American Society for Radiation Oncologist
bDFS	biochemical Disease-Free Survival
CS	Clinical Stage
CT Scan	Computed Tomography Scan
CTCAE	Common Terminology Criteria for Adverse Events
CTV	Clinical Treatment Volume
DRE	Digital Rectal Exam
DVH	Dose Volume Histogram
EB	External Beam
EBRT	External Beam Radiation Therapy
ECOG	Eastern Cooperative Oncology Group
EQD	Equivalent Dose
GEE	Generalized Estimating Equation
GI	Gastrointestinal
GTV	Gross Tumor Volume
GU	Genitourinary
Gy	Gray
HDR	High-Dose Rate
I-125	Iodine 125
IMRT	Intensity Modulated Radiotherapy
IR	Intermediate Risk
IV	Intravenous
LDR	Low-Dose Rate
LR	Low Risk
MRI	Magnetic Resonance Imaging
MV	Mega Voltage
NCI	National Cancer Institute
OPC	Objective Performance Criteria
OPC	Objective Performance Criteria
Pa-103	Palladium – 103
PE	Physical Exam
PSA	Prostate-Specific Antigen
PTV	Planning Target Volume
PTV	Primary Tumor Volume
QOL	Quality of Life
RP	Radiculär Prostatectomy
RT	Radiation Therapy
SBRT	Stereotactic Body Radiotherapy
SV	Seminal Vesicle
UCSF	University of California San Francisco

## PROTOCOL SUMMARY

### Title

**A Prospective Evaluation of Hypofractionated Stereotactic Body Radiotherapy (SBRT) for Low and Intermediate Risk Prostate Cancer**

### Objectives

The *primary* objectives of this study are:

- To determine, in both low-risk and intermediate-risk cohorts, the rates of acute and late grade 3 or higher gastrointestinal and genitourinary toxicity observed during an initial 24 month follow up.
- To estimate the rate of biochemical Disease-Free Survival (bDFS), Phoenix and ASTRO definitions, at 2 years following hypofractionated SBRT for low and intermediate risk prostate cancer. Failure occurs when the PSA is  $\geq 2$  ng/ml more than the lowest PSA measurement before the current one, with no backdating.

The *secondary* objectives of this study are to:

To determine

1. the rate of local failure: proportion of patients with local disease progression at 2 years
2. rate of distant failure: proportion of patients with metastatic disease at 2 years
3. rate of disease-free survival: median time from start of treatment until disease progression
4. rate of disease-specific survival: death due to prostate cancer (excludes patients that relapse with inactive disease)
5. overall survival: median length of time from either the date of diagnosis or the start of treatment for a disease, such as cancer, that patients diagnosed with the disease are still alive.
6. quality of life (QOL) in generic and organ-specific domains using the FACT-G assessment tool

### Patient population

In order to be eligible for this study, patients will have a histologically confirmed adenocarcinoma of the prostate which is a clinical stage T1b-T2b, Nx-0 and Mx-0. The following combinations will be allowed:

- Gleason score 2-6 and PSA  $\leq 20$
- Gleason score 7 and PSA  $\leq 10$

All patients will have an ECOG Performance Status of 0-1 and have had no prior prostate radiation or definitive therapy.

### Number of patients

200

### Study design and methodology

This is a phase II study.

**Treatments administered**

SBRT:

Patients will receive 36.25 Gy in 5 fractions (7.25 Gy/fx) delivered over a 2-week period.

**Efficacy data collected**

The following evaluations will be performed to assess the efficacy of stereotactic body radiation therapy (SBRT) in low and intermediate risk prostate cancer:

- the rate of local failure
- rate of distant failure
- rate of disease-free survival
- rate of disease-specific survival
- overall survival
- quality of life (QOL) in generic and organ-specific domains

**Safety data collected**

The following evaluations will be conducted to assess the safety of radiosurgery:

- Recording of all toxicity data per NCI CTCAE version 3.0

## 1.0 Background

Prostate cancer is the most common malignancy in men; an estimated 219,000 cases will be diagnosed in the United States in 2007. PSA screening has led to earlier stage diagnoses; in 1998, 92% of prostate cancers were diagnosed with clinically organ-confined disease. According to the NCI Consensus Conference in 1988, and the Prostate Cancer Panel of the American Urological Association in 1995, treatment options (ie standard of care options) that should be discussed with each patient in this category include radical prostatectomy, external beam radiation therapy (RT), interstitial brachytherapy and watchful waiting.

First attempts to treat organ-confined prostate cancer with radiotherapy yielded poor biochemical disease free outcomes, as insufficient doses were delivered to the target. Since the 1980's, conformal RT techniques have been developed which reduced dose to the surrounding organs, allowing the safe delivery of greater doses to the prostate. Conformal RT has been achieved either through 3-dimension conformal external beam RT (3D CRT), or through prostate brachytherapy. These techniques have yielded disease-free outcomes similar to those seen with radical prostatectomy (see table 1), although not without toxicity.

Modern external beam radiotherapy uses three-dimensional treatment planning, delivering RT to the prostate through typically 5-7 coplanar beams. With intensity modulated radiotherapy (IMRT), dose is modulated through each of these beams. Due to variations in patient positioning and internal organ motion, the position of the prostate cannot be accurately determined using exterior skin marks. Placing gold fiducials in the prostate, and imaging prior to treatment deliver reduces targeting error, but this typically does not account for movement within a given treatment session. Such intrafractional movement can be substantial: in one study it was estimated at 2mm, 6mm, and 7mm in the left-right, anterior-posterior, and cranial-caudal directions, respectively. Radiation oncologists account for this uncertainty by adding a margin to the intended target. Expanding radial dimensions to create a "planning target volume" (PTV) increases the volume of surrounding normal structures in the high dose region, potentially increasing toxicity.

In the last decade, transperineal ultrasound-guided brachytherapy has gained popularity for treating organ-confined prostate cancer. Brachytherapy allows the delivery of conformal, high-dose radiotherapy to the prostate, with a rapid dose fall-off outside of the implanted region. Favorable long-term outcomes using permanent iodine-125 (I-125) and palladium-103 (Pd-103) implants have been reported in numerous studies. High-dose rate (HDR) brachytherapy has been used in the treatment of prostate cancer since the 1980's. Catheters are placed temporarily in the prostate, and then loaded with a high-dose Iridium-192 source, delivering a few fractions of very high-dose RT. Initial protocols employing HDR combined conventionally fractionated external beam RT with an HDR boost. More recent reports have employed HDR as monotherapy. Adjusting for pre-treatment risk factors, these studies yield bDFS outcomes at least as favorable to those seen with LDR brachytherapy or conformal dose-escalated RT or IMRT (see table 1). Indeed, a prospective, non-randomized study from William Beaumont Hospital comparing HDR monotherapy versus LDR brachytherapy (Pd-103) showed a superior 5-year event-free survival (98% vs. 85%, p=0.01) and a trend towards improved freedom from cancer failure (98% vs.

92%,  $p=0.1$ ) in the HDR cohort. The same group showed acute and late toxicity, potency, and QOL following HDR brachytherapy was more favorable than either LDR brachytherapy or conformal external beam RT. The rate of impotence three years following HDR was 16%, compared to 45% following LDR brachytherapy.

**Table 1. bDFS Outcomes for Low-Risk Prostate Cancer using Current Standard of Care Treatments (brachytherapy, external beam radiation, and surgery)**

Rx	Details	Institution	# pts	Median f/u yrs	5-yr bDFS: Definition			Ave ‡
					Phoenix	ASTRO		
HDR	45-50Gy + 2-4 fx boost	Seattle, Kiel, Beaumont 	46	5		96%		92%
	36Gy + 5.5-6Gy x 4 boost	CA Endocurie 	70	7.25	93%	90%		
HDR	Monotx: 6-7.25Gy x 6	CA Endocurie 	117 #	8		96%		97%
	Monotx: 9.5Gy x 4	Beaumont 	95 †	4.2		98%		
LDR	Monotx: 145Gy I125	RTOG 9805  phase II	95	5.3	99%	93%		88%
	Monotx: I125 & Pd103	11 inst meta-analysis 	1444	5.25	86%	88%		
EB	IMRT: 70Gy, 2.5Gy/fx	Clev Clin  hypofract	36	5.5	97%	97%		97%
	IMRT: 81Gy, 1.8Gy/fx	MSKCC 	203	7	92%	84%		
	3dRT/IMRT: >72Gy	9 instit meta-analysis 	70	5.7		79%		
	3dRT/IMRT: 70-76Gy	9 instit meta-analysis 	231	6.3	94%			83%
	3dConformal: 78Gy proton bst to 79.2Gy	MDA rand dose-esc  MGH, Loma Linda 	32 116	>5 5.5	93% 96%	92% 80.5%		
RP	Institutions	Author	#pts	f/u yrs	Definition	bDFS	Ave ‡	
	Baylor	Hull 	299	3.9	PSA $\geq$ 0.4	92.5%		
	ClevClinic & MSKMercy	Kupelian 			PSA $\geq$ 0.2	92%		
	Univ Pennsylvania	D'Amico 	322	5	ASTRO	88%		
	Hopkins	Han 	899 *	5.9	PSA $\geq$ 0.2	98%		

\*Number of patients, bDFS estimated based on proportions within each risk group. #75% low risk, 25% intermediate; †Included T2b in low-risk group. ‡Weighted average, using ASTRO or stated definition.

Radiation oncologists fractionate RT dose to reduce toxicity to surrounding normal tissues. For most cancers, by delivering dose over several weeks, equivalent cancer-killing effect is achieved with reduced long-term toxicity. The effect of dose fractionation on both cancer and normal tissues can be estimated using the “linear-quadratic model”. In this model, the alpha-beta ratio reflects the response of normal tissues or cancers to changes in RT dose per fraction. Most cancers respond to RT as do rapidly-dividing normal tissues (e.g., skin or mucous membranes), and thus have high  $\alpha/\beta$  ratios, in the 10-12 Gy range. Tissues with lower  $\alpha/\beta$  ratios are more sensitive to large dose per fraction (also known as hypofractionated) RT.

The favorable control rates observed with hypofractionated RT led radiobiologists to reconsider  $\alpha/\beta$  ratio of prostate carcinoma. Several researchers have concluded that prostate cancer has an unusually low  $\alpha/\beta$  ratio of about 1.5Gy. Another analysis estimated the  $\alpha/\beta$  ratio was between 3.1-3.9 Gy; a more recent study of 3756

patients yielded a ratio between 2.6 and 3.7Gy. A low  $\alpha/\beta$  ratio is consistent with other biologic properties of prostate cancer: an unusually long tumor doubling times, and a very low proportion of proliferating cells. Although the actual  $\alpha/\beta$  ratio for prostate cancer is debated, the accepted range of 1–4 Gy appears to be similar to, or smaller than the  $\alpha/\beta$  ratios for late effects in the surrounding normal tissues (3-5 Gy). Thus a therapeutic gain could be achieved by hypofractionation. Indeed, this approach should result in equivalent or improved cancer control with reduced toxicity.

In 1951, Lars Leksell, a Swedish neurosurgeon, first described radiosurgery: the use of converging beams of ionizing radiation to non-surgically ablate intracranial lesions. He later developed the “GammaKnife”, which focuses 201 collimated Co-60 beams at a single isocenter. A metal frame was fixed to the patient’s skull, providing both a reference for treatment, and a means to rigidly fix the skull. Another method of delivering stereotactic radiotherapy uses multiple isocentric arcs from a linear accelerator equipped with a small collimator; again the patient rigidly immobilized.

In the 1990s a novel device was developed at Stanford University for delivering stereotactic radiosurgery without the need for rigid immobilization. This device, called “CyberKnife”, uses a lightweight x-band linear accelerator mounted on an industrial robot. The system uses a pair of amorphous silicon detectors to gather orthogonal fluoroscopic images of the patient. Bony landmarks or implanted fiducials near the target are continuously imaged, and the system’s computer automatically makes adjustments to account for variations in set-up or patient movement. The target can be treated from about 1200 different directions, using coplanar or non-coplanar beams. The CyberKnife can treat static intra- and extra-cranial sites with sub-millimeter accuracy.

Radiosurgery should be ideal for treating prostate cancer because 1) targeting accuracy for static targets is excellent, with an error of about 1mm, 2) it can adjust for intra-fractional organ motion, reducing the volume of the target PTV and therefore the dose to surrounding organs, 3) by using over one-hundred non-conplanar beams, the dose gradient between the prostate and surrounding tissues may be superior to that achieved with conventional linear accelerators, and 4) the radiobiology of prostate cancer may favor large dose per fractions.

As discussed above, the current standard of care for early localized prostate cancer include radical prostatectomy, conventional external beam radiation (IMRT), interstitial brachytherapy, and occasionally watchful waiting. With increasing evidence of a low  $\alpha/\beta$  ratio for prostate adenocarcinoma, there has been an interest in using larger radiation fractions and shorter treatment schedules (fewer fractions). Stereotactic radiosurgery was thus a logical choice to attain such goals, given its ability to deliver a highly conformal dose of radiation with rapid fall-off—allowing the sparing of nearby organs at risk. Hypofractionation and SBRT present several potential advantages. Ideally, tumor control may be increased for a given level of late complications. Conversely, late complications may be reduced for a given level of tumor control. Patient convenience would increase with fewer fractions compared with standard EBRT courses that extend between 7-9 weeks. Equipment utilization and staffing may be more efficient, which may translate to increased cost efficiency.

Given the relatively recent interest in SBRT for prostate cancer (the past 2-3 years), there are only a few institutions that have, to date, reported outcomes following SBRT for prostate cancer. This paucity of data highlights the need for trials such as the one proposed here. With the exception of Virginia Mason Medical Center and Stanford University, the majority of experiences are available in abstract form only. A Phase I/II trial of SBRT at Virginia Mason Medical Center using a linear accelerator and fiducial marker system was reported by Madsen et al.. Forty low-risk patients received 33.5 Gy in 5 fractions (BED2Gy = 78 Gy; a/b = 2 Gy). Six noncoplanar fields using a linear accelerator and daily stereotactic localization of the prostate using three radio- opaque fiducial markers were used. A margin of 4 to 5 mm from block edge to the prostate was used for treatment. Patients were placed on a diet to minimize gas and took daily simethicone to reduce rectal dilatation and movement during treatment. Before each fraction, orthogonal images were obtained and analyzed for the position of the fiducial markers. An automated computer program (Isoloc 5.2; Northwest Medical Physics Equipment, Linwood, WA) was used to calculate the necessary position shifts before treatment. With a median follow-up of 41 months, 4-year PSA nadir + 2 FFBF was 90%, and ASTRO (three rises) FFBF was 70%. Acute Grade 1 or 2 toxicity RTOG toxicity was 49% (genitourinary) and 39% (gastrointestinal). There was a single incidence of Grade 3 genitourinary toxicity. Late Grade 1 or 2 toxicity was 45% (genitourinary) and 37% (gastrointestinal). No late Grade 3 or higher toxicity was reported. At Stanford University forty-one patients received 36.25 Gy in 5 fractions (BED2Gy = 90.6 Gy; a/b = 1.5 Gy). Patients were treated with implantable gold fiducials for daily localization, as well as intrafraction tracking performed every 30–90 s. With a median follow-up of 33 months, no patient has experienced biochemical failure (ASTRO or nadir + 2). There were 2 patients with RTOG Grade 3 late urinary toxicity and none with Grade 3 rectal toxicity. There was no Grade 4 toxicity. The first 21 patients received daily treatment; the remaining 20 patients were treated every other day. Quality of life scored according to the Expanded Prostate Cancer Index Composite suggested improved rectal complications with every-other-day dosing.

The Korean Institute of Radiological and Medical Sciences reported on forty-four patients that received 32–36 Gy in 4 fractions, with the exception of 1 patient who received 24 Gy in 3 fractions. There were 10 low-risk (PSA <10 ng/mL, Gleason score <6, Stage T1b-T2a), 9 intermediate-risk (PSA 10–20 ng/mL, Gleason score 7), and 25 high-risk patients (PSA >20 ng/mL or Gleason score >8). With a median followup of 13 months, overall survival at 3 years was 100%, with a 3-year FFBF rate of 78%. Fourteen patients experienced Grade 1 or 2 acute rectal toxicity, and 17 patients experienced Grade 1 or 2 bladder toxicity. There were no Grade 3 or greater acute toxicities. Late toxicity was not reported. Ten patients were treated by the Radiation Medical Group of San Diego and received 38 Gy in 4 fractions. Very preliminary results were reported; the median pretreatment PSA level was 6.9 ng/mL, and at 4 months after treatment it had decreased to 0.7 ng/mL in the first 8 patients. Toxicity was not detailed. A 21st Century Oncology Center in Fort Myers, FL reported on twenty-two patients receiving 36.25 Gy in 5 fractions. The Common Toxicity Criteria for Adverse Effects, version 3.0, were used to assess toxicity at intervals from 1 to 12 months after treatment. Twenty-two patients were reported, of whom 18 had been followed for at least 1 month. During treatment, 3 patients reported dysuria and 5 urinary hesitancy, all Grade 1 toxicities. At 1 month, 1 patient reported continued dysuria and hesitancy, and 4

patients reported frequency and urgency. During treatment, 5 patients reported diarrhea, and 2 reported proctitis. At 1 month, 1 patient reported continued proctitis, Grade 1.

Patients followed for more than 3 months returned to baseline urinary and rectal function. No reporting of clinical outcomes was made.

## 2.0 Objective

### PRIMARY OBJECTIVES:

- 2.1 The primary safety goal of this study is to determine, in both low-risk and intermediate-risk cohorts, the rates of acute and late grade 3-5 gastrointestinal and genitourinary toxicity observed during the initial 24 months following hypofractionated SBRT for prostate cancer. Patients will be followed for at least 5 years but possibly as long as 10 years, but initially we will strive to obtain 2 year follow-up results.
- 2.2 The primary efficacy goal is to document the rate of biochemical Disease-Free Survival (bDFS), Phoenix and ASTRO definitions, at 2 years. As above, we will ultimately aim for at least 5 years of follow-up but possibly as long as 10 years, with a short term goal of 2 years.

### SECONDARY OBJECTIVES:

- 2.3 To measure the following in the study population: Rates of local failure, distant failure, disease-free survival, disease-specific survival, and overall survival; quality of life (QOL) in generic and organ-specific domains.

## 3.0 Investigational Plan

### 3.1 Initial Evaluation

Prior to enrollment all patients will be evaluated with a physical exam (including DRE), review of pathology and laboratory values to confirm diagnosis, and baseline imaging studies. In addition, since there are many feasible treatment options for men with early, localized prostate cancer a detailed conversation will be had regarding all possible treatment options comprising the current standard of care. Specifically, the treating physician will discuss conventional EBRT using IMRT to doses  $\geq 75.6$  Gy using 1.8 Gy daily fractions, low dose rate brachytherapy using Cesium-131, radical prostatectomy, and watchful waiting for those men with short life expectancy. This will be an important and crucial part of the study, since long-term data is not available for SBRT as a primary treatment for prostate cancer. In other words, it is not currently accepted as standard of care, and is therefore experimental. This will be detailed in laymen's terms in the consent form as well (summarized on page 16 of consent). All participants will be made aware of the high success rates with the current standards of care (5 year disease free survivals approaching 100% as seen in Table 1) and the chance that such high rates could theoretically be compromised by participating in this trial since 5 year follow-up using SBRT is not currently available.

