## 7.2 SAMPLE SIZE:

7.2.1 PRIMARY SAFETY OBJECTIVE: The study is designed to test the null hypothesis that the acute and late GI/GU toxicity rate 2 years following treatment is less than 10% versus the alternative hypothesis that the toxicity rate is greater than or equal to 10%. If we end up with 200 eligible patients, there will be 99% probability, or statistical power, of identifying excessive toxicity if the true

toxicity rate is 20%, at the one-sided significance level ( $\alpha$ ) 0.05. The intervention will be considered to be safe if the acute and late GI/GU toxicity rate 2 years following treatment is not above 10%

7.2.2 PRIMARY EFFICACY OBJECTIVE: The study is powered to compare 2-year bDFS rates observed with SBRT to 2-year bDFS rates reported with dose-escalated external beam RT. In Beaumont's monotherapy HDR series treating patients, 5-yr ASTRO bDFS was 97.5%; in Demanes' series of 75% LR and 25% IR, this was 96%. We would expect Phoenix outcomes to be slightly higher than ASTRO outcomes at 5 years. Since SBRT delivers doses similar to HDR monotherapy, a conservative estimate of the success rate for SBRT is 97.5%. In LR patients, prospective studies from Memorial Sloan Kettering (203 patients, 81Gy) and MD Anderson (32 patients, 78Gy) demonstrated 5-yr bDFS (Phoenix definition) of 92% and 92%, respectively. Thames' 9-institution review of 231 dose-escalated (70-76Gy) LR patients reported 94% 5-yr Phoenix bDFS. Thus, an objective performance criteria (OPC) for low-risk patients treated with dose-escalated external beam RT is 92% 5-yr bDFS. If we assume the SBRT success rate is 97%, a sample size of 200 patients will provide 99% power to test superiority of SBRT against this OPC with 80% power at the 1-sided 5% significance level. If we assume the SBRT success rate is 96%, then the power will be 78%.

7.2.3 TOTAL AND RELATIVE ENROLLMENT: Per above sections 7.2.1-7.2.2, we plan to accrue 200 eligible patients to compare the 2-year bDFS rate observed with SBRT to the 2-year OPC rate, and to establish acceptable toxicity. The test cohort will be closed to accrual once requisite enrollment is achieved: 200 total patients.

7.2.4 ACCRUAL RATE: The accrual rate will be 5–6 patients / month over 2 years.

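### Section 3.1 has all participants told that standard care gives 5-year disease-free survival near 100% and cites Table 1, which shows 79% to 99% biochemical control in low-risk series

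*Combined protocol and SAP*

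**What the plan says.** Section 3.1 sets out the conversation held before enrolment and treats it as a crucial part of the study. The alternatives to be discussed are IMRT to at least 75.6 Gy in 1.8 Gy fractions, LDR brachytherapy with Cesium-131, radical prostatectomy and, for men with short life expectancy, watchful waiting. It then states: "All participants will be made aware of the high success rates with the current standards of care", and gives those rates as "5 year disease free survivals approaching 100% as seen in Table 1". Men are also told of a chance that such rates "could theoretically be compromised by participating in this trial since 5 year follow-up using SBRT is not currently available". The same paragraph says of SBRT that "it is not currently accepted as standard of care, and is therefore experimental".

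The table it relies on is titled "bDFS Outcomes for Low-Risk Prostate Cancer using Current Standard of Care Treatments". Its averages are footnoted "Weighted average, using ASTRO or stated definition".

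Two other places bear on the statement. Section 7.2.2 concludes that "an objective performance criteria (OPC) for low-risk patients treated with dose-escalated external beam RT is 92% 5-yr bDFS". Section 1.0 reports an SBRT series of 40 low-risk men at 33.5 Gy in 5 fractions, in which "4-year PSA nadir + 2 FFBF was 90%, and ASTRO (three rises) FFBF was 70" per cent. It also reports 41 men at 36.25 Gy in 5 fractions with no biochemical failure at a median of 33 months.

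**The concern.** Section 3.1 specifies what men hear when they choose between SBRT and established treatment, and it names its source. If the source does not bear out the figure, following the plan as written gives men a number that the protocol cannot support.

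There are three further mismatches:
- **Endpoint.** Table 1 reports biochemical control. Section 3.1 calls it disease-free survival, which section 6.4.3.2 defines separately, counting any measure of disease or death.
- **Population.** Table 1 is titled low-risk. The trial also enrols intermediate-risk men, who would be given the same figure.
- **The SBRT side.** The paragraph says that 5-year follow-up is lacking, but does not mention the shorter-term control rates that section 1.0 already gives.

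**Working it through.** **Step 1: does Table 1 reproduce its own averages?** Inputs are the numbers of patients and the 5-year bDFS percentages in Table 1, using the ASTRO or stated definition as the footnote directs. The formula is sum(n × rate) / sum(n).

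| Group | Calculation | Result | Printed |
|---|---|---|---|
| HDR boost | (46×96 + 70×90)/116 | 92.4% | 92% |
| HDR monotherapy | (117×96 + 95×98)/212 | 96.9% | 97% |
| LDR | (95×93 + 1444×88)/1539 | 88.3% | 88% |
| Hypofractionated IMRT | one series, n=36 | 97.0% | 97% |
| Conventional external beam | (203×84 + 70×79 + 32×92 + 116×80.5)/421 | 82.8% | 83% |

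All five agree. The table is internally sound, and the fault lies in the phrase that summarises it.

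**Step 2: the figures the table does not print.**
- Conventional external beam, Phoenix entries: (203×92 + 231×94 + 32×93 + 116×96)/582 = 93.6%.
- LDR, Phoenix entries: (95×99 + 1444×86)/1539 = 86.8%.
- Prostatectomy, the three series with a number of patients: (299×92.5 + 322×88 + 899×98)/1520 = 94.8%. A fourth series, at 92%, has no number and is left out.

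**Step 3: does any reading give a figure near 100%?** Table 1 holds 23 percentages, from 79% to 99%. Five are 97% or higher and seven are 90% or lower. The two averages of 97% belong to HDR monotherapy and to one 36-patient hypofractionated IMRT series, and section 3.1 lists neither as an option.

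For the options it does list, biochemical failure by 5 years is:
- conventional external beam: 100 − 82.8 = 17.2% (ASTRO) or 100 − 93.6 = 6.4% (Phoenix);
- LDR: 100 − 88.3 = 11.7% (ASTRO) or 100 − 86.8 = 13.2% (Phoenix);
- prostatectomy: 100 − 94.8 = 5.2%.

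The row closest to the IMRT schedule in section 3.1 (81 Gy at 1.8 Gy per fraction, n=203) shows 92% by Phoenix and 84% by ASTRO. Cesium-131 and watchful waiting have no row.

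**Step 4: how the protocol reads the same table elsewhere.** Section 3.3 uses Table 1 to argue that HDR and hypofractionated results are better than those of conventional fractionation, and that a higher equivalent dose may be needed to reach 96–98%. Section 7.2.2 sets 92% for low-risk external beam and plans to show superiority over it. Neither fits a summary in which standard care as a whole is close to 100%.

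**Step 5: population.** The footnotes say that one HDR series was 25% intermediate risk and that another counted T2b as low risk. No row reports intermediate-risk men separately.

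**The case against.** The strongest reply is that this is loose wording in a paragraph that is otherwise candid. Section 3.1 says that long-term SBRT data are lacking, that SBRT is experimental and that control may be compromised. Table 1 does contain entries of 97% to 99%. The 83% for external beam is the ASTRO figure; by Phoenix, the definition that section 7.2.2 uses for its benchmark, it is about 94%. The 92% in section 7.2.2 covers low-risk external beam only and does not summarise all standards of care. Overstating standard care also makes the alternatives look better, so that part of the statement does not favour enrolment.

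Most of this stands, and it limits the point. It does not rescue the phrase: by either definition, no average for a listed option reaches 97%, and the table is cited as showing what it does not show.

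A reader might go further in three ways that the documents do not support:
- **That men are told the loss of control is merely theoretical.** Section 3.1 speaks of a chance, gives the reason and calls the treatment experimental.
- **That consent rests on wrong figures.** The consent pages were not available, and no entry in Table 1 is shown to be wrong. The conversation is also not limited to this one phrase.
- **That section 1.0 shows SBRT to be inferior.** The 90% and 70% are 4-year rates at 33.5 Gy. The 78% at 3 years comes from a series in which 25 of 44 men were high-risk and the schedule was almost entirely 32–36 Gy in 4 fractions. The series at 36.25 Gy in 5 fractions had no failures, though follow-up was short. Subtracting these from Table 1's 5-year rates would mix doses, time points and populations.

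**Conclusion.** The inconsistency is real. Section 3.1 attributes to Table 1 a disease-free survival near 100%, while the table shows 5-year biochemical control of 79% to 99% in low-risk series. The averages for the listed options that have rows run from about 83% to 95%, depending on modality and failure definition. The statement also carries a low-risk biochemical result over to all participants under a different endpoint name. The omission of section 1.0's SBRT results from the paragraph is a lesser, related gap.

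The conclusion rests on the table rows as extracted, which the agreement of all five printed averages supports. The prostatectomy average is less firm: its printed value could not be read, the size and rate of its largest series are footnoted as estimates, and its series use different PSA thresholds. The point concerns participant information only. Power, sample size, significance level and the efficacy and safety thresholds are unaffected.

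**What to change.** In section 3.1:

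1. Replace the near-100% phrase with Table 1's rates by modality and PSA-failure definition: conventional external beam 83% (ASTRO) or 94% (Phoenix), LDR 88% (ASTRO) or 87% (Phoenix), prostatectomy about 95%, with the overall range of 79% to 99%.
2. Label them as 5-year biochemical control in low-risk men. State that Table 1 gives no separate intermediate-risk result, and that its LDR series used I-125 and Pd-103, not Cesium-131.
3. Beside the sentence on possible loss of control, add the results from section 1.0 with their context: 90% (nadir + 2) and 70% (ASTRO) at 4 years in 40 low-risk men at 33.5 Gy in 5 fractions, and no failures in 41 men at 36.25 Gy in 5 fractions at a median of 33 months. If the 78% at 3 years is given, say that 25 of the 44 men were high-risk and that the schedule differed.
4. Draw no numerical differences between these series and Table 1.
5. Check that the consent text agrees.

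The cost is one paragraph and a check of the consent form, using figures already in the protocol. The downside is a less simple message for participants.
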